11.3.1 Hematology and blood chemistry parameters

Observed values for each planned hematology and blood chemistry parameter will be summarized for Baseline, Study Entry, and each scheduled visit during the Evaluation Period for which laboratory parameters were assessed, Last Value, EDV, and FV. Change from Baseline will be summarized for all post-Baseline time points including EV. Only laboratory parameters planned per protocol will be summarized; results for laboratory parameters not planned per the protocol will only be provided in subject data listings.

The number and percentage of subjects with an on-treatment potentially clinically significant treatment-emergent (PCST) value, PCST low value, and PCST high value will be summarized. This summary will consider all assessments after the first dose of BRV and prior to or on the date of the last dose of BRV. Percentages will be relative to the number of subjects with an on-treatment assessment.

Additionally, the number and percentage of subjects with a PCST value, PCST low value, and PCST high value will be summarized for Baseline, Study Entry, each visit during the Evaluation Period for which laboratory parameters were scheduled to be assessed, EDV, Last Value, and FV. Percentages for each parameter and time point will be relative to the number of subjects with a value at that time point.

PCST criteria (Sections 13.3.1 and 13.3.2) are based on Food and Drug Administration (FDA) Division of Neuropharmacologic Drug Products guidelines with some UCB-defined additions.

Creatinine clearance, when available from the central laboratory, will be provided in subject data listings only and will not be summarized.

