13.3 PCST criteria

13.3.1 Hematology parameters

| Parameter | UCB Conventional Units | SI Units | CF |
|------------------------|---|---|---|
| Hematocrit | For 1 m to < 6 m: ≤ 25% For 6 m to < 2 y: ≤ 27% For 2 y to < 4 y: ≤ 29% For 4 y to < 12 y: ≤ 32% (Female[F]); ≤ 35% (Male [M]) For ≥ 12 y: ≤ 32% (F); ≤ 37% (M) | For 1 m to < 6 m: ≤ 0.25 For 6 m to < 2 y: ≤ 0.27 For 2 y to < 4 y: ≤ 0.29 For 4 y to < 12 y: ≤ 0.32 (F); ≤ 0.35 (M) For ≥ 12 y: ≤ 0.32 (F); ≤ 0.37 (M) | 0.01 |
| Hemoglobin | For < 6 m: ≤ 9.7 g/dL For 6 m to < 12 y: ≤ 10.0 g/dL For ≥ 12 y: ≤ 9.5 g/dL (F); ≤ 11.5 g/dL (M) | For < 6 m: ≤ 97 g/L For 6 m to < 12 y: ≤ 100 g/L For ≥ 12 y: ≤ 95 g/L (F); ≤ 115 g/L (M) | 10 |
| Platelets | ≤ 75 x 10 ⁹ /L or ≥ 700 x 10 ⁹ /L | ≤ 75 x 10 ⁹ /L or ≥ 700 x 10 ⁹ /L | Not applicable (N/A) |
| White Blood Cell (WBC) | For < 17 y: ≤ 3.0 x 10 ⁹ /L or ≥ 20 x 10 ⁹ /L; For ≥ 17 y: ≤ 2.8 x 10 ⁹ /L or ≥ 16 x 10 ⁹ /L; | For < 17 y: ≤ 3.0 x 10 ⁹ /L or ≥ 20 x 10 ⁹ /L; For ≥ 17 y: ≤ 2.8 x 10 ⁹ /L or ≥ 16 x 10 ⁹ /L; | N/A |
| Red Blood Cell (RBC) | For < 17 y: ≤ 2.5 x 10 ⁶ /mm ³ For ≥ 17 y: ≤ 2.0 x 10 ⁶ /mm ³ (F); ≤ 2.5 x 10 ⁶ /mm ³ (M) | For < 17 y: ≤ 2.5 x 10 ¹² /L For ≥ 17 y: ≤ 2.0 x 10 ¹² /L (F); ≤ 2.5 x 10 ¹² /L (M) | 1 |
| Eosinophils | ≥ 10% or ≥ 0.7 x 10 ⁹ /L | ≥ 0.10 or ≥ 0.7 x 10 ⁹ /L | 0.01 or N/A |
| Neutrophils | ≤ 15% or ≤ 1.0 x 10 ⁹ /L | ≤ 0.15 or ≤ 1.0 x 10 ⁹ /L | 0.01 or N/A |
| Basophils | ≥ 5% or ≥ 0.4 x 10 ⁹ /L | ≥ 0.05 or ≥ 0.4 x 10 ⁹ /L | 0.01 or N/A |
| Monocytes | ≥ 20% or ≥ 1.5 x 10 ⁹ /L | ≥ 0.20 or ≥ 1.5 x 10 ⁹ /L | 0.01 or N/A |
| Lymphocytes | For 1 m to < 6 m: ≤ 22% or ≥ 80% ≤ 2.1 x 10 ⁹ /L or ≥ 8.5 x 10 ⁹ /L For 6 m to < 2 y: ≤ 15% or ≥ 80% ≤ 1.5 x 10 ⁹ /L or ≥ 7.5 x 10 ⁹ /L For 2 y to < 12 y: ≤ 12% or ≥ 80% ≤ 1.0 x 10 ⁹ /L or ≥ 7.5 x 10 ⁹ /L For 12 y to < 17 y: ≤ 10% or ≥ 80% ≤ 0.5 x 10 ⁹ /L or ≥ 5.5 x 10 ⁹ /L For ≥ 17 y: ≤ 10% or ≥ 80% ≤ 0.5 x 10 ⁹ /L or ≥ 4.5 x 10 ⁹ /L | For 1 m to < 6 m: ≤ 0.22 or ≥ 0.80 ≤ 2.1 x 10 ⁹ /L or ≥ 8.5 x 10 ⁹ /L For 6 m to < 2 y: ≤ 0.15 or ≥ 0.80 ≤ 1.5 x 10 ⁹ /L or ≥ 7.5 x 10 ⁹ /L For 2 y to < 12 y: ≤ 0.12 or ≥ 0.80 ≤ 1.0 x 10 ⁹ /L or ≥ 7.5 x 10 ⁹ /L For 12 y to < 17 y: ≤ 0.10 or ≥ 0.80 ≤ 0.5 x 10 ⁹ /L or ≥ 5.5 x 10 ⁹ /L For ≥ 17 y: ≤ 0.10 or ≥ 0.80 ≤ 0.5 x 10 ⁹ /L or ≥ 4.5 x 10 ⁹ /L | 0.01 N/A 0.01 N/A 0.01 N/A 0.01 N/A 0.01 N/A |

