13.3.2 Blood chemistry parameters

| Parameter | UCB Conventional Units | SI Units | CF |
|-----------------------------|---|---|--------|
| AST (SGOT) | ≥ 3 times of ULN | ≥ 3 times of ULN | N/A |
| ALT (SGPT) | ≥ 3 times of ULN | ≥ 3 times of ULN | N/A |
| ALP | For < 17 y: ≥ 2 times of ULN, if normal range adjusted to the age range; For ≥ 17 y: ≥ 3 times of ULN | For < 17 y: ≥ 2 times of ULN, if normal range adjusted to the age range; For ≥ 17 y: ≥ 3 times of ULN | N/A |
| GGT | ≥ 3 times of ULN, if baseline value ≤ 3 times of ULN | ≥ 3 times of ULN, if baseline value ≤ 3 times of ULN | N/A |
| BUN | ≥ 30 mg/dL | ≥ 10.71 mmol/L | 0.357 |
| Urea | ≥ 60 mg/dL | ≥ 10.02 mmol/L | 0.167 |
| Creatinine | For < 17 y: ≥ 1.5 mg/dL; For ≥ 17 y: ≥ 2.0 mg/dL | For < 17 y: ≥ 132.6 umol/L; For ≥ 17 y: ≥ 176.8 umol/L | 88.4 |
| Creatinine clearance (calc) | For < 12 y: < 70 ml/min (Schwartz) ^(a) For ≥ 12 y: < 70 ml/min (Cockcroft) ^(b) | For < 12 y: < 70 ml/min (Schwartz) ^(a) For ≥ 12 y: < 70 ml/min (Cockcroft) ^(b) | N/A |
| Total bilirubin | ≥ 2.0 mg/dL | ≥ 34.2 umol/L | 17.1 |
| Glucose | ≤ 50 mg/dL or ≥ 180 mg/dL | ≤ 2.775 mmol/L or ≥ 9.99 mmol/L | 0.0555 |
| Total Protein | For ≥ 1 m to < 6 m: ≤ 3.6 g/dL or ≥ 7.8 g/dL For ≥ 6 m to < 17 y: ≤ 4.7 g/dL or ≥ 9.5 g/dL For ≥ 17 y: ≤ 4.5 g/dL or ≥ 9.0 g/dL | For ≥ 1 m to < 6 m: ≤ 36 g/L or ≥ 78 g/L For ≥ 6 m to < 17 y: ≤ 47 g/L or ≥ 95 g/L For ≥ 17 y: ≤ 45 g/L or ≥ 90 g/L | 10 |
| Albumin | For < 17 y: ≤ 2.4 g/dL or ≥ 6.5 g/dL For ≥ 17 y: ≤ 2.5 g/dL or ≥ 6.5 g/dL | For < 17 y: ≤ 24 g/L or ≥ 65 g/L For ≥ 17 y: ≤ 25 g/L or ≥ 65 g/L | 10 |
| Globulin | For < 17 y: ≤ 1.2 g/dL or ≥ 5.0 g/dL For ≥ 17 y: ≤ 1.5 g/dL or ≥ 5.0 g/dL | For < 17 y: ≤ 12 g/L or ≥ 50 g/L For ≥ 17 y: ≤ 15 g/L or ≥ 50 g/L | 10 |
| Sodium | For < 17 y: ≤ 120 mEq/L or ≥ 155 mEq/L For ≥ 17 y: ≤ 115 mEq/L or ≥ 155 mEq/L | For < 17 y: ≤ 120 mmol/L or ≥ 155 mmol/L For ≥ 17 y: ≤ 115 mmol/L or ≥ 155 mmol/L | 1 |
| Potassium | For < 17 y: ≤ 3.0 mEq/L or ≥ 6.5 mEq/L For ≥ 17 y: ≤ 3.0 mEq/L or ≥ 5.8 mEq/L | For < 17 y: ≤ 3.0 mmol/L or ≥ 6.5 mmol/L For ≥ 17 y: ≤ 3.0 mmol/L or ≥ 5.8 mmol/L | 1 |
| Calcium | For < 17 y: ≤ 7 mg/dL or ≥ 11.5 mg/dL For ≥ 17 y: ≤ 7 mg/dL or ≥ 15.5 mg/dL | For < 17 y: ≤ 1.75 mmol/L or ≥ 2.875 mmol/L For ≥ 17 y: ≤ 1.75 mmol/L or ≥ 3.875 mmol/L | 0.25 |

This document cannot be used for marketing authorizations, clinical trial extensions or variations thereof.

| | | | |
|--|---|---|--------|

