13.3.4 Vital signs and body weight

| | |
|------------|---|
| Pulse rate | 
For 1 m to < 12 m: ≤ 110 bpm and a decrease of ≥ 20 bpm from baseline or ≥ 180 bpm and an increase of ≥ 20 bpm from baseline
 
For 12 m to < 3 y: ≤ 90 bpm and a decrease of ≥ 20 bpm from baseline or ≥ 150 bpm and an increase of ≥ 20 bpm from baseline
 
For 3 y to < 12 y: ≤ 65 bpm and a decrease of ≥ 20 bpm from baseline or ≥ 130 bpm and an increase of ≥ 20 bpm from baseline
 
For 12 y to < 17 y: ≤ 60 bpm and a decrease of ≥ 20 bpm from baseline or ≥ 120 bpm and an increase of ≥ 20 bpm from baseline
 
For ≥ 17 y: ≤ 50 bpm and a decrease of ≥ 30 bpm from baseline or ≥ 120 bpm and an increase of ≥ 30 bpm from baseline
 |
|------------|---|

bpm=Beats per minute.

| | |
|--------------------------|---|
| Systolic blood pressure | 
For 1 m to < 12 m: < 60 mmHg and a decrease of > 20 mmHg from baseline or > 110 mmHg and an increase of > 30 mmHg from baseline
 
For 12 m to < 6 y: < 70 mmHg and a decrease of > 20 mmHg from baseline or > 120 mmHg and an increase of > 30 mmHg from baseline
 
For 6 y to < 13 y: < 70 mmHg and a decrease of > 20 mmHg from baseline or > 130 mmHg and an increase of > 30 mmHg from baseline
 
For 13 y and < 17 y: < 90 mmHg and a decrease of > 20 mmHg from baseline or > 140 mmHg and an increase of > 30 mmHg from baseline
 
For ≥ 17 y: < 90 mmHg and a decrease of > 30 mmHg from baseline or > 180 mmHg and an increase of > 40 mmHg from baseline
 |
| Diastolic blood pressure | 
For 1 m to < 12 m: < 40 mmHg and a decrease of > 15 mmHg from baseline or > 60 mmHg and an increase of > 20 mmHg from baseline
 
For 12 m to < 6 y: < 45 mmHg and a decrease of > 15 mmHg from baseline or > 80 mmHg and an increase of > 20 mmHg from baseline
 
For 6 y to < 13 y: < 50 mmHg and a decrease of > 15 mmHg from baseline or > 85 mmHg and an increase of > 20 mmHg from baseline
 
For 13 y to < 17 y: < 55 mmHg and a decrease of > 20 mmHg from baseline or > 90 mmHg and an increase of > 30 mmHg from baseline
 
For ≥ 17 y: < 50 mmHg and a decrease of > 20 mmHg from baseline or > 105 mmHg and an increase of > 30 mmHg from baseline
 |
| Weight | 
For < 17 y: < 3% or > 97% of the normal body weight growth curve ranges for the age at date of weight assessment ^(a) and gender;
 
For ≥ 17 y: change of ≥ 7% of baseline weight
 |

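### Haematology and blood chemistry PCST counts call values treatment-emergent without checking Baseline (GGT excepted), so new and pre-existing abnormalities cannot be told apart

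*SAP*

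**What the plan says.** SAP 11.3.1 sets out an overall on-treatment summary in which "subjects with an on-treatment potentially clinically significant treatment-emergent (PCST) value, PCST low value, and PCST high value will be summarized". It defines the window, "This summary will consider all assessments after the first dose of BRV and prior to or on the date of the last dose of BRV", and the denominator, "Percentages will be relative to the number of subjects with an on-treatment assessment". Neither sentence sets aside subjects who were beyond the limit at Baseline.

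The criteria are in SAP 13.3.1 (haematology) and 13.3.2 (blood chemistry). They are fixed limits by age and sex, or multiples of the upper limit of normal. Creatinine is typical: "For < 17 y: ≥ 1.5 mg/dL; For ≥ 17 y: ≥ 2.0 mg/dL". The one exception is GGT: "≥ 3 times of ULN, if baseline value ≤ 3 times of ULN".

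The same section then tabulates the flag by time point, starting before treatment: "PCST high value will be summarized for Baseline, Study Entry, each visit during the Evaluation Period for which laboratory parameters were scheduled to be assessed".

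Baseline is the pretreatment Baseline of the previous study (Protocol 13.1.3; SAP 3.3), defined separately for each laboratory parameter.

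**The concern.** PCST is expanded in the SAP as potentially clinically significant treatment-emergent, and Protocol 13.1.3 promises summaries of treatment-emergent laboratory abnormalities. A reader will take the on-treatment percentage to mean abnormalities that arose after treatment began. For all these parameters but GGT, the rule measures something else: the share of subjects with any on-treatment value beyond a limit, whether or not they were beyond it beforehand.

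Long-term safety is the primary objective and the study has one arm. A controlled trial would carry roughly similar baseline abnormality in both arms, so a comparison would remain interpretable. Here there is no comparator, and the new-onset rate, which is what a long-term safety study is asked for, cannot be read from the table.

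**Working it through.** **1. Count the criteria.** SAP 13.3.1 has 10 haematology rows and 13.3.2 has 21 chemistry rows: 10 + 21 = 31. One (GGT) has a baseline condition, so 31 − 1 = 30 do not.

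SAP 11.3.1 summarises only parameters planned in the protocol. Set against Protocol 11.1.14:
- Haematology: 10 planned parameters have a limit (MCV, MCH and MCHC have none).
- Chemistry: 14 planned analytes have a limit (inorganic phosphorus has none; calculated creatinine clearance is listed only).
- Total: 10 + 14 = 24, of which 24 − 1 = 23 lack a baseline condition.

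**2. Compare with the SAP's other emergence rules.**
- Qualitative urinalysis (13.3.3) requires an upward shift of at least two degrees from baseline.
- Adult pulse (13.3.4) requires a limit and a change: "≤ 50 bpm and a decrease of ≥ 30 bpm from baseline or ≥ 120 bpm and an increase of ≥ 30 bpm from baseline". Blood pressure follows the same pattern. Adult weight requires a change of at least 7% from baseline.
- TEAEs (11.2.1) exclude events that began before the first dose in this study.
- Within the liver tests the flag has two meanings. A subject stable at 4 times the upper limit for both ALT and GGT since before treatment is PCST for ALT and not for GGT.

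**3. Check whether another table recovers the distinction.** SAP 11.3.1 also gives PCST counts at Baseline and Study Entry, and change-from-Baseline statistics. These are separate summaries at each time point. They do not show whether the subjects flagged on treatment are those flagged at Baseline. No shift table or cross-classification is planned in that section; only the subject listings would show it.

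**4. Illustrate the size.** The plan states no PCST rate, so there is no figure to reproduce. Inputs:
- N = 668 enrolled (SAP 2.4), used for scale; the number with on-treatment laboratory data is not given.
- b = share beyond the limit at Baseline (assumed 1% to 5%).
- r = share of those with at least one qualifying on-treatment value (assumed 50% to 90%).
- i = new on-treatment incidence among the rest (assumed 1% to 3%).

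Pre-existing cases = N·b·r. New cases = N·(1−b)·i. The SAP count is their sum, and the pre-existing share is br / [br + (1−b)i], which does not depend on N.

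| b | r | i | Pre-existing | New | SAP count (% of 668) | Pre-existing share |
|---|---|---|---|---|---|---|
| 1% | 50% | 3% | 668 × 0.01 × 0.5 = 3.3 | 668 × 0.99 × 0.03 = 19.8 | 23.2 (3.5%) | 14% |
| 3% | 90% | 1% | 668 × 0.03 × 0.9 = 18.0 | 668 × 0.97 × 0.01 = 6.5 | 24.5 (3.7%) | 74% |
| 5% | 90% | 1% | 668 × 0.05 × 0.9 = 30.1 | 668 × 0.95 × 0.01 = 6.3 | 36.4 (5.4%) | 83% |

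The first and last rows are the extremes of the assumed grid. Restricted to subjects not beyond the limit at Baseline, the reported rates would be 3.0%, 1.0% and 1.0%.

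**The case against.** Several points on the other side stand.

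- **Scope.** A reader might infer that all laboratory PCST counts are affected. They are not: qualitative urinalysis is referenced to baseline. Nor is every subject abnormal at Baseline counted, only one who also has a qualifying on-treatment value.
- **Consequence.** A reader might infer that the primary safety results are overstated. The primary safety variables are TEAEs, withdrawals due to AEs and SAEs (SAP 2.2.1.1). Laboratory tests are an other safety variable (2.2.1.2), everything is descriptive, and the error runs towards over-reporting harm.
- **Size.** A reader might want a definite inflation factor. The documents do not support one. Full persistence gives an upper value: with b = 2% and i = 3%, 0.02 + 0.98 × 0.03 = 4.9%; at 50% persistence it is 0.02 × 0.5 + 0.98 × 0.03 = 3.9%. Some limits are extreme (adult sodium at or below 115 mEq/L, platelets at or below 75 × 10⁹/L), and subjects with laboratory values that may affect their safety are excluded (Protocol 9.2). For such rows the baseline prevalence may be close to zero.
- **No single definition is breached.** The vital-sign and urinalysis rules require a change from baseline, but not that the subject was below the limit beforehand. A systolic pressure going from 185 to 230 mmHg is PCST under 13.3.4. Only the GGT rule has the form proposed here.
- **A bare exclusion loses information.** Removing subjects abnormal at Baseline would also remove those who then worsen. This is a good objection, and the fix has to meet it.

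The defence that Baseline counts and changes from Baseline are also shown helps only partly, because those summaries do not link the same subjects across time. That the criteria rest on FDA division guidelines does not settle the matter either: 11.3.1 says the sponsor made additions, and the source of a limit does not make crossing it treatment-emergent.

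**Conclusion.** The concern holds for haematology and blood chemistry. For 23 of the 24 protocol-planned parameters with a limit, the plan as written reports a pre-existing abnormality as treatment-emergent whenever a qualifying value also occurs on treatment. No planned summary table lets a reader separate these from new cases. Tabulating PCST at Baseline confirms that for these parameters the flag works as an absolute limit.

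This conclusion rests on the text alone. The size does not: the range of 14% to 83% depends on the assumed prevalence, persistence and incidence, will differ by parameter, and should not be quoted as an estimate for this study. It is worth correcting before the tables are produced. It does not call the primary safety variables into question.

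**What to change.** - **(a) Definition, SAP 11.3.1.** Report as on-treatment PCST only subjects who did not meet the same criterion (same parameter, same direction) at Baseline. The denominator is subjects with an on-treatment value who either did not meet the criterion at Baseline or have no Baseline value. Keep subjects with missing Baseline in both numerator and denominator, and give their number in a footnote.
- **(b) Shift table.** For each parameter add Baseline category by worst on-treatment category, so that subjects abnormal at Baseline, including those who worsen, remain visible.
- **(c) Labels and reference point.** Head the Baseline column potentially clinically significant rather than PCST. State that an abnormality first arising during the previous study, after its pretreatment Baseline, counts as emergent relative to that Baseline and is shown at Study Entry. This needs saying because TEAEs are anchored to the first dose in this study, whereas laboratory Baseline is earlier.

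No new data are needed, since Baseline is already defined per parameter (SAP 3.3). The cost is SAP wording, a small programming change, one extra set of tables and a slightly smaller denominator. At the assumed prevalences, and if all 668 had on-treatment data, the denominator would fall to between 668 × 0.99 = 661 and 668 × 0.95 = 635.

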### **9.3.1 Withdrawal Criteria**

Subjects are free to withdraw from the study at any time, without prejudice to their continued care.

Stopping rules and discontinuation criteria for individual subjects may be for example:

- Withdrawal for safety reasons by the Investigator; occurrence of status epilepticus, appearance of a more severe type of seizure, liver enzymes significant increase, and any other significant safety reason.
- Subject and/or Investigator does not think that the investigational drug is effective (i.e., lack or loss of efficacy).
- Lost to follow-up.
- Withdrawal of consent for personal reasons; not related to AE or lack/loss of efficacy.
- Other reason that has to be specified in the CRF.

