#### ***11.1.26 End of Study***

The end of the subject's participation in the study will be confirmed on the subject's status evaluation section of the CRF. All data about the subject's status (study completion or reason for early study termination) will be recorded. It will be specified:

- Whether the subject completed (participated until the study was stopped) or prematurely discontinued the study

A subject will be considered lost to follow-up following 2 unsuccessful documented attempts to contact the subject (e.g. by telephone).

If a subject will not continue with the study drug, the Investigator will first schedule an Early Discontinuation Visit which will be followed by a progressive down-titration of the study drug. The dose decrease can be made by steps of a maximum of 50 mg/day on a weekly basis. A last down-titration step at 20 mg/day for 1 week will be included prior to the study-drug free period. At the end of the down-titration period, a Down-Titration Phone Call will occur for subjects having down-titrated from doses higher than 20 mg/day. The Down-Titration Period will be followed by a period free of study drug at the minimum of 2 weeks and a maximum of 4 weeks and subsequently the Final Visit will occur.

When the time point is reached at which the study will be terminated by the sponsor (as defined in Section 8.4), subjects will discontinue the study drug, following the above

described down-titration process or will be converted without down-titration to commercial BRV, when and where available. Alternatively, subjects may transition to another BRV study or be initiated without down-titration in a managed access program, named patient program, compassionate use program, or similar type of access program as allowed per country-specific legal and regulatory requirements

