3.2 Analysis time points

3.2.1 First and last dose of BRV

Unless otherwise noted, all references to the first dose of BRV in this SAP refer to the first dose of BRV during N01199 (ie, not the first dose of BRV from the previous study in which subjects participated in prior to N01199). Unless otherwise noted, all references to the last known dose of BRV in this SAP refer to the last dose of BRV taken across any study periods (ie, not necessarily the last dose of BRV during the Evaluation Period).

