3.2.4 Study periods

The study is divided into 3 periods: Evaluation Period, Down-Titration Period, and Post-Treatment Period. A subject is classified as “discontinued” if the subject has a termination case report form (CRF) or has an early discontinuation visit (EDV). A subject is classified as “completed” if this subject completes the full extent of the study as defined in the protocol at database lock.

A “discontinued” subject can be potentially slotted into the 3 periods of the study. The following algorithms will be used to slot the subject appropriately into the Evaluation Period, Down-Titration Period, and Post-Treatment Period.

- For Evaluation Period, the start date is the date of first dose of BRV, and the following algorithm is used to determine the end date:
 - If the subject enters the Down-Titration Period, then the date of EDV is the end date;
 - If the subject does not enter the Down-Titration Period but meets 1 of the following criteria, the Evaluation Period ends on date of last dose of BRV:
 - Without an EDV but having a termination CRF,
 - With an EDV and having a termination CRF,
 - With an EDV and the date of EDV prior to the database lock date and having no termination CRF.
- A subject is considered entering Down-Titration Period only if the subject has an EDV and at least 1 dose of study drug after the date of EDV, the start date of Down-Titration Period is set as 1 day after the date of EDV, and the Down-Titration Period ends on date of last dose of BRV. A subject without an EDV but having a termination CRF or with an EDV but without any dosing of study drug after the EDV will not have the Down-Titration Period, and no artificial Down-Titration Period will be created for analysis.
- A subject is considered entering the Post-Treatment Period if the subject has at least 1 contact (scheduled visit, unscheduled visit, or telephone contact) after the date of last dose of BRV. The Post-Treatment Period starts 1 day after date of last dose of BRV irrespective of entering the Down-Titration Period, and there is no end date.

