3.2.6 Last Value on BRV Treatment

Last Value for QOLIE-31-P, HADS, EQ-5D, and socio-professional data is the last assessment strictly after the date of first dose of BRV and up to and including the YEV at the end of the second year and any EDVs for subjects who did not complete through the YEV at the end of the second year.

Last Value for clinical laboratory parameters, vital signs, and ECGs is the last available result obtained after the first dose of BRV and prior to or on the date of last dose of BRV. All scheduled and unscheduled assessments within this time period will be considered. Last Value will be determined separately for each laboratory parameter.

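### The overall on-treatment safety summaries and Last Value close on the date of last dose, so discontinuation-visit results count for subjects who tapered but not for subjects who had already stopped

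*SAP*

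**What the plan says.** SAP 11.3.1 defines the overall summary of potentially clinically significant treatment-emergent (PCST) hematology and chemistry values over "all assessments after the first dose of BRV and prior to or on the date of the last dose of BRV", with subjects having at least one such assessment as the denominator. SAP 11.3.2 (urinalysis), 11.4.1 (vital signs and body weight) and 11.4.2 (ECG) use the same window and denominator rule. For laboratory parameters, vital signs and ECG, SAP 3.2.6 defines Last Value as "the last available result obtained after the first dose of BRV and prior to or on the date of last dose of BRV". None of these sections allows any time after the last dose.

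SAP 3.2.1 says that, unless otherwise noted, references to the last known dose "refer to the last dose of BRV taken across any study periods", so doses taken during down-titration count.

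On the order of events, Protocol 11.1.26 says that "the Investigator will first schedule an Early Discontinuation Visit which will be followed by a progressive down-titration of the study drug". SAP 2.3 and 3.2.4 also provide for discontinuation without a taper. A subject "with an EDV but without any dosing of study drug after the EDV will not have the Down-Titration Period", and the Evaluation Period then ends on the date of last dose.

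Separate by-visit tables in SAP 11.3.1 cover "each visit during the Evaluation Period for which laboratory parameters were scheduled to be assessed, EDV, Last Value, and FV", with every subject who has a value at that time point as the denominator. SAP 11.3.2, 11.4.1 and 11.4.2 contain equivalent by-visit tables.

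**The concern.** The EDV is the planned end-of-treatment safety assessment for a subject who leaves. Under the zero-lag window, whether its result enters the overall abnormality percentage depends on how the subject stopped. A subject who tapers has later doses, so the EDV is on treatment. A subject who stopped a day or more earlier has the same visit classed as off treatment.

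These two groups may differ. Stopping before the EDV departs from the protocol's planned order, and Protocol 9.3.1 gives as examples of safety withdrawal a "liver enzymes significant increase, and any other significant safety reason". If subjects who stop on their own or suddenly carry more abnormalities, the across-visit percentage and the Last Value changes would lean toward normal. Long-term safety is the primary objective, and the across-visit summary is the only one that gives a subject-level incidence of any on-treatment abnormality.

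**Working it through.** The plan states no figure on this point. The check is date logic, followed by the visit schedule and an illustration of scale.

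**1. Where an EDV result goes, by date of last dose** (SAP 3.2.1, 3.2.4, 3.2.6, 11.3.1, 11.3.2, 11.4.1, 11.4.2)

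| Case | Overall on-treatment count and denominator | Eligible as Last Value | By-visit EDV column |
|---|---|---|---|
| (a) EDV, then taper: last dose after EDV | Yes | Yes | Yes |
| (b) Last dose on the EDV date | Yes | Yes | Yes |
| (c) Last dose at least 1 day before EDV, no taper | No | No | Yes |

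Only case (c) is affected. The EDV column cannot simply be added to the overall count, because the results of cases (a) and (b) already sit in both.

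**2. What else is in the window for a case (c) subject** (Protocol Tables 5:1 and 5:2; SAP 11.3, 11.4.1, 11.4.2)

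- Laboratory tests are scheduled at full and yearly visits, EDV and Final Visit. For subjects from the confirmatory studies these fall at Months 2, 6, 12, 18 and 24, so the gaps are 6 − 2 = 4 months and then 6 months. A subject who stops before Month 2 has no scheduled in-window laboratory result.
- ECGs are scheduled at yearly visits, EDV and Final Visit, the first yearly visit being Month 12. On that schedule a subject who stops before Month 12 has no scheduled in-window ECG and leaves the ECG denominator unless an unscheduled one was done. Protocol 11.1.12 indicates that ECGs were more frequent before they were cut to once a year.
- Vital signs are taken at every evaluation visit, so scheduled gaps are at most 3 months and the point is weaker there.

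**3. Other rules in the SAP**

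- The ECG listing of clinically significant findings (11.4.2) runs from the first dose with no end date. A case (c) subject can be listed there and be absent from the on-treatment ECG count.
- The TEAE definition (11.2.1) has no upper time limit.
- Last Value for the questionnaires (3.2.6) admits EDVs without reference to the last dose.

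**4. Pharmacokinetics** (Protocol 6.2: half-life about 8 hours in young healthy men)

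- At 24 hours: 24 / 8 = 3 half-lives, leaving 0.5³ = 12.5% of the drug.
- Five half-lives: 5 × 8 = 40 hours, or 40 / 24 = 1.7 days.

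A result on the day after the last dose can still reflect exposure, yet it is outside the window.

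**5. Scale, for illustration only**

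The documents do not give the number in case (c). Assuming 1% to 10% of the 668 enrolled (SAP 2.4): 668 × 0.01 = 6.7 and 668 × 0.10 = 66.8, so about 7 to 67 subjects. For a parameter with an assumed 2% rate (668 × 0.02 = 13.4 cases) and no excess in case (c), those subjects would hold 6.7 × 0.02 = 0.1 to 66.8 × 0.02 = 1.3 cases, that is 1% to 10% of the total. The share rises only if their abnormality rate is higher, which the documents do not show.

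**The case against.** The strongest reply is that the window does what its name says. A result after the last dose is not on treatment, and SAP 3.2.4 starts the Post-Treatment Period one day after the last dose. This stands: the rule is coherent and contradicts nothing in the SAP.

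A reader might infer that these EDV results are not counted at all. The documents do not support that. The by-visit tables show PCST values and ECG findings at the EDV, and listings are provided. An abnormality reported as an adverse event is caught by the open-ended TEAE definition, and TEAEs, SAEs and withdrawals due to adverse events are the primary safety variables. Laboratory, vital-sign and ECG results are other safety variables, summarized descriptively.

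A reader might also take SAP 3.2.4 as proof that case (c) is common. It is not. Its wording covers subjects with no dose after the EDV, which includes a last dose on the EDV date, and that is inside the window. Protocol Table 5:1 and section 11.2.5 give an ordinary reason for no taper: transition to another study or an access program.

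On direction, a subject withdrawn for raised liver enzymes may well have had them measured before stopping. That result, scheduled or unscheduled, is in the window. This weakens the bias argument without removing it, because some abnormalities would first be seen at the EDV.

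The reply does not explain why subjects who tapered and subjects who had just stopped should be handled differently at the same visit, nor does it supply an across-visit incidence that includes both.

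**Conclusion.** The point holds in a limited form. EDV results obtained a day or more after the last dose are omitted from the overall on-treatment abnormality incidence, its denominator and Last Value, for laboratory, urinalysis, vital-sign, weight and ECG data. They remain visible in the EDV columns and listings. The date logic follows from the SAP text alone and needs no assumption.

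The number affected and the size of any bias cannot be derived from the documents; the 7 to 67 subjects above rest on an assumed 1% to 10%. The likely direction is toward fewer abnormalities, which is plausible but not shown.

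It is tempting to go further and claim that a large share of abnormal cases is lost. At the top of the range, if 10% of the 67 had a new abnormality, that would be 6.7 of 13.4 cases, or half. But this leaves 13.4 − 6.7 = 6.7 cases among 668 − 66.8 = 601 others, or 1.1%, so it presupposes a rate about nine times higher (10 / 1.1) in subjects who stopped before the EDV. Nothing in the documents supports such a ratio.

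This is a gap in a supporting safety summary that is worth closing because it is cheap. It does not threaten the primary safety variables.

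**What to change.** Either change would do.

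1. **Short lag.** In SAP 3.2.6, 11.3.1, 11.3.2, 11.4.1 and 11.4.2, count assessments, including the EDV, up to a short prespecified lag after the last dose. Justify the lag from the half-life: five half-lives is 40 hours, which argues for about 2 days. A lag of 7 days would be 168 / 8 = 21 half-lives and would bring in largely drug-free values. SAP 3.2.4 must be aligned, since the Post-Treatment Period now starts one day after the last dose; state which rule governs these safety measurements.
2. **Added summary.** Keep the current window and add, for each parameter, the number and percentage of subjects with any abnormality on treatment or at the EDV, counting each subject once. This leaves the period definitions untouched.

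In both cases, report how many subjects had an EDV after the last dose, and keep the Final Visit as the drug-free assessment.

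The cost is SAP wording and some reprogramming; no new data are needed. The downside is that a few values taken shortly after the last dose are counted together with on-treatment values.
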